9.1.3 Missing Data

Every attempt will be made to avoid missing data. All subjects will be used in the analyses, as per the analysis sets using all of the available non-missing data. [REDACTED] subscales that were collected during protocol version 1.0-3.0 will be calculated, and the missing responses will be handled using the built-in scoring tool.

Safety data will not be subject to any imputation and will be summarized on an observed basis.

The following conventions will be used for missing adverse event (AE) dates ([Section 9.1.3.1](#)), and missing prior and concomitant medication dates ([Section 9.1.3.2](#)) for determining the TEAEs or for determining prior and concomitant medication. The actual date will not be replaced by the imputed date.

9.1.3.1 Adverse Events Onset Date

If the AE onset date is completely missing in which the day, month, and year are all missing, do not impute a date but consider it as TEAE, unless the AE end date is before the initiation of treatment, in which case the AE will be considered prior.

For the partial AE onset date and time,

- If the year is present, but the month and day are missing:
 - If year of AE onset = year of initiation of the treatment, then set the month and day to the month and day of initiation of the blinded treatment

Statistical Analysis Plan (Methods)
Study 547-PPD-304

Sage Therapeutics, Inc.
CONFIDENTIAL

- If year of AE onset < year of initiation of the treatment, then set the month and day to December 31.
- If year of AE onset > year of initiation of the treatment, then set the month and day to January 1.
- If the year and month are present, but the day is missing:
 - If year and month of AE onset = year and month of initiation of the treatment, then set the day to the day of initiation of the treatment.
 - If year and month of AE onset < year and month of initiation of the treatment, then set the day to the last day of month
 - If year and month of AE onset > year and month of initiation of the treatment, then set the day to the first day of the month
- If the year and day are present and the month is missing:
 - If year of AE onset = year of initiation of the treatment and
 - if day \geq the day of initiation of the treatment, then set the month to the month of initiation of the treatment
 - if day < day of initiation of the treatment, and
 - If the month of initiation of the treatment = December, then set the month to the month of initiation of the treatment, i.e. December.
 - If the month of initiation of the treatment < December, then set the month = the month of initiation of the treatment +1.
 - If year of AE onset < year of initiation of the treatment, then set the month to December.
 - If year > year of initiation of the treatment, then set the month to January.
- If the year and day are present and the month is missing, then treat it as if the day is missing, and only the year is present. Follow the imputation rules for “year is known, but the month and day is unknown”.
- When the year is missing, but the month and/or day is known, treat this date as missing; do not impute.

The general rule is to impute the AE onset date as close as to the initiation of treatment date, with a preference to after the initiation of the treatment date. If the imputed AE onset date is after the AE stop date, then set the onset date to the AE stop date.

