3 INTRODUCTION

This Statistical Analysis Plan (SAP) is based on the approved clinical study protocol Version 4.0 dated 20 December 2019.

The purpose of the SAP is to describe in detail the statistical methodology and the statistical analyses to be conducted for data presentation for Study 547-PPD-304, a multicenter, open-label study evaluating doses up to 90 mcg/kg/h of brexanolone in adolescent female subjects with postpartum depression.

All patients who received the active study treatment brexanolone will be presented, which includes patients who were randomized in the earlier versions of the protocol (Protocol Version 1.0, dated 23 January 2018, Version 2.0, dated 11 September, 2018, and Version 3.0 dated 03 June 2019), and received the active study treatment, as well as the patients who are enrolled under Protocol Version 4.0, the open-label study.

In addition, for the patients enrolled under the double blinded protocol versions (Protocol Version 1.0, dated 23 January 2018, Version 2.0, dated 11 September, 2018, and Version 3.0 dated 03 June 2019), all of their data will be presented according to their randomized treatment arms (placebo and brexanolone).

All analyses and summary outputs will be generated using SAS® version 9.4 (or higher).

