5 STUDY ENDPOINTS

5.1 Primary Endpoint

- Incidence of treatment-emergent adverse events (TEAEs)

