9.4.2 Adverse Events

The analysis of AEs will be based on the concept of TEAEs. A TEAE is defined as an AE with onset on or after the start of study drug infusion, or any worsening of a pre-existing medical condition/AE with onset on or after the start of study drug infusion.

All adverse events will be coded using MedDRA version 23.0 or higher and summarized by SOC and PT. Multiple occurrences of an AE are counted only once per subject per SOC and per PT for summary tables. Incidences will be presented in order of decreasing frequency of the brexanolone group by SOC and PT. Incidences will also be presented in order of decreasing frequency of the brexanolone group by PT only. In addition, summaries will be provided by severity (mild, moderate, severe) and by causality (related, not related) to study drug (see protocol section 12.2.2 for definitions). TEAEs leading to treatment discontinuation and study discontinuation and Serious AEs (SAEs) (see protocol section 12.2.1.2 for definition) with onset after the start of randomized infusion will also be summarized.

Summary tables of TEAEs will be presented by treatment and will summarize the number and percentage of subjects for the following:

- Any TEAE
- TEAEs by maximum severity to study drug (mild, moderate, severe)
- Treatment-emergent serious AEs (SAEs)
- TEAEs leading to discontinuation of study drug
- TEAEs leading to withdrawal from study
- AEs of special interest (AESIs), which include:
 - Excessive sedation
 - Loss of consciousness
 - Any sedation-related AE that leads to dose reduction, interruption, or termination

Subjects will be counted only once within each SOC and PT at the maximum severity in the following order: severe, moderate, and mild. An AE with missing severity will be considered as a severe AE. The incidences will be presented by descending frequency of SOC and then, within a SOC, by descending frequency of PT based on the subject count, and in alphabetical order of PT if the incidence within a PT is a tie.

Subjects will be counted only once within each SOC and PT at the strongest relationship to study drug in the following order: related, not related to study drug. If the relationship between the AE and the study drug is determined to be “possible” or “probable”, the event will be considered as related to the study drug. An AE with missing relationship to study drug will be considered as related to study drug.

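### Two conflicting rules cover an AE onset with only the month missing, and for some December starts one of them makes a certain pre-dose onset a TEAE (minor)

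*SAP*

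**What the plan says.** SAP Section 9.1.3.1 sets out how partial AE onset dates are imputed. Two bullets at the same level have the same condition: year and day present, month missing.

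- **First rule.** For an onset in the year of treatment start, a recorded day on or after the start day takes the start month. An earlier day takes the following month, except for a December start: "If the month of initiation of the treatment = December, then set the month to the month of initiation of the treatment, i.e. December".
- **Second rule.** For the same pattern, "then treat it as if the day is missing, and only the year is present". The year-only rule then applies, and it assigns a same-year onset to the treatment start date.

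Two general statements close the section. One is to "impute the AE onset date as close as to the initiation of treatment date, with a preference to after" treatment start. The other is a stop-date cap: "If the imputed AE onset date is after the AE stop date, then set the onset date to the AE stop date".

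Section 9.1.3 says that these conventions serve to determine TEAEs, and adds: "The actual date will not be replaced by the imputed date". Section 9.4.2 states: "A TEAE is defined as an AE with onset on or after the start of study drug infusion". Worsening of a pre-existing condition after the start of infusion also qualifies. Section 5.1 makes TEAE incidence the primary endpoint.

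**The concern.** Both rules cannot be followed. Two programmers could each comply with the SAP and derive different onset dates for the same record. Because the imputed date is used only to classify the event, the conflict matters where it changes TEAE status.

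In one situation it does. With a December start, a same-year onset and a recorded day before the start day, no month places the onset on or after dosing. The first rule has a December branch for exactly this case and keeps the onset pre-dose. The second rule moves it to the start date and makes it a TEAE, against the definition in Section 9.4.2.

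At stake is an over-count of the primary endpoint in small columns. About 20 brexanolone subjects are planned (Section 6.2). For subjects enrolled under the blinded protocol versions, "all of their data will be presented according to their randomized treatment arms" (Section 3), so those columns are likely to be smaller still.

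**Working it through.** **Inputs.** The two rules, the year-only rule and the stop-date cap come from Section 9.1.3.1, and the TEAE definition from Section 9.4.2. Comparison is by date, so an onset on the start date counts as on or after the start. The SAP gives no figure of its own to reproduce.

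**Examples**

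| Start | Recorded day | First rule | Second rule |
|---|---|---|---|
| 15 December | 10, same year | 10 December, not a TEAE | 15 December, TEAE |
| 20 June | 10, same year | 10 July, TEAE | 20 June, TEAE |

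**Same-year grid, 2019.** Every start date is crossed with every recorded day from 1 to 31.

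- Combinations: 365 × 31 = 11,315.
- The first rule gives a date that does not exist (such as 31 June) in 207, leaving 11,315 − 207 = 11,108.
- The rules give the same date only when the recorded day equals the start day (365 combinations), so 11,108 − 365 = 10,743 differ in date.
- TEAE status differs in 465, all with December starts. A start on day s has s − 1 earlier days, and 0 + 1 + … + 30 = 465, out of 31 × 31 = 961 December combinations.
- In all 465, every possible date is before dosing. The first rule gives no TEAE and the second gives a TEAE.

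The 2020 grid has 11,346 combinations, 179 without a valid first-rule date, and again 465 with different status.

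**Other onset years.** For start dates in 2018 to 2020 and an onset one year earlier or later, status differs in 0 of (365 + 365 + 366) × 31 × 2 = 67,952.

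**Screening limit.** Assume AEs are recorded only from the 14-day screening period of Section 6.1. The affected combinations are then the sum over December start days of min(s − 1, 14). Days 1 to 15 give 105 and days 16 to 31 give 16 × 14 = 224, so 329 remain.

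**Stop-date cap.** For the 465 combinations, every stop date was tried from the December onset day to 32 days after the start (study Day 33, the end of the Day 30 window).

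- Stop before dosing: 4,960 cases, 0 still in conflict.
- Stop on or after dosing: 465 × 33 = 15,345 cases, all still in conflict.

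A missing stop date or an ongoing event also leaves the conflict in place.

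**Effect of one subject.** A preferred term moves by 1/N, which is 1/20 = 5.0 points in a column of 20. Section 9.4.2 also plans a table of preferred terms above 5% in any group. In a column of 19 or fewer, going from 0 to 1 subject crosses that limit (1/19 = 5.3%). In a column of 20 to 39, going from 1 to 2 crosses it (1/20 = 5.0% does not exceed it; 2/39 = 5.1% does).

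**The case against.** **Rarity.** A wrong label needs a missing month with a known day and year, a start on 2 to 31 December, a same-year onset, an earlier recorded day, a stop date that is missing or not before dosing, and no post-dose worsening. The SAP gives no sign that such a record exists, and the analysis is descriptive with no test. This stands, and it is why the point is minor. The 10,743 differing dates have no stated consequence, because the dates only classify.

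**The 5% table.** All TEAEs are tabulated anyway, so this table is only a display subset, and any misclassified subject would move a rate by 1/N. Both statements are true. They limit the effect but do not remove it.

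**The general rule.** On distance alone, the second rule always gives a date at least as close to treatment start. Over-counting also fits the SAP's cautious conventions: a completely missing onset counts as a TEAE unless the event ended before treatment, and a missing relationship counts as related. But those conventions deal with uncertainty. They cannot justify moving an onset that is certainly pre-dose. Nor does the general rule say which bullet governs. Outside the December case, preferring the first rule is a matter of choice, with no effect on TEAE status.

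**The remedy.** Section 9.1.3.1 already covers the other partial-date patterns, so it is hard to see what else the second bullet could have been meant for. A month-end fallback for impossible dates is a new convention that gives up the recorded day. Both remarks are fair. The fallback does no harm, because it leaves TEAE status unchanged.

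**Conclusion.** The concern holds. Section 9.1.3.1 gives two incompatible instructions for one pattern and no order of precedence. For December starts with a same-year onset and an earlier recorded day, the second instruction contradicts both the TEAE definition and the first rule's own December branch.

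The size is 465 discordant calendar combinations per year, or 329 if AE recording starts at screening. The error always runs towards over-counting. It disappears if a pre-dose stop date is recorded, and it does not matter if the event is a TEAE anyway through post-dose worsening. The SAP does not give the number of December starts or of onsets with a missing month, so no expected count can be stated, but it should be small. This is a low-severity correction to a rule that feeds the primary endpoint.

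**What to change.** Delete the second bullet, so that the first rule, which respects the recorded day, governs. If the second bullet was meant for another case, correct its condition instead.

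Add one line: if the first rule gives a day that does not exist in the chosen month (for example start 31 January, recorded day 30), use the last day of that month. This date is before the start in 0 of 207 cases in 2019 and 0 of 179 in 2020, and falls no later than study Day 30. Moving on to the next month that has the day would pass Day 33 in 190 of 207 and 166 of 179 cases.

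The cost is one bullet deleted or corrected and one line added, in the SAP and in the date-derivation program. Data collection does not change.

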9.1.3.2 Prior and Concomitant Medications Date

If the start date (or end date) of a medication is completely missing in which the year is unknown, then the start date (or end date) will not be imputed.

For the partial start date of medication,

- If the year is present and the month and day are missing, set the month and day to January 1.
- If the year and day are present and the month is missing, set the month to January.

Statistical Analysis Plan (Methods)
Study 547-PPD-304

Sage Therapeutics, Inc.
CONFIDENTIAL

- If the year and month are present and the day is missing, set the day to the first day of the month.
- If the imputed start date of medication is after the non-imputed end date of medication, then the start date will be set to the end date of medication.

For the partial end date of medication,

- If the year is present and the month and day are missing, set the month and day to December 31.
- If the year and day are present and the month is missing, set the month to December.
- If the year and month are present and the day is missing, set the day to the last day of the month.
- If the imputed end date of medication is before the non-imputed start date of medication, then the end date will be set to the start date of medication.

If both the start date and end date are imputed, and the imputed end date of medication contradicts with the imputed start date of medication, the general rule is to set the imputed month or day (either stop or start) to the non-imputed month and day (either stop or start) such that they will not contradict each other. Then consider the following:

- If the imputed end month = imputed start month, and
 - If the imputed end day $<$ imputed start day, then the end day will be set to the start day of medication.
- If the imputed end month $<$ imputed start month, and
 - If the imputed end day \geq imputed start day, then the end month will be set to the start month of medication.
 - If the imputed end day $<$ imputed start day
 - If the start month of the medication is not December, then the end month will be set to the start month of medication +1
 - If the start month of the medication = December, then the end month will be set to the start month of medication (December) and the end day will be the start day of the medication.

9.2 Background Characteristics

9.2.1 Subject Disposition

The analyses of subject disposition will use all subjects who provided written informed consent to the study.

The summaries of subject disposition will include the number and percentage of subjects who were screened, screen failed, enrolled, randomized, received brexanolone injection or placebo, subjects who completed the study, who prematurely withdrew from the study, primary reasons for not completing the study, who completed infusion, who discontinued infusion prematurely, and primary reasons for discontinuing treatment. Study completion summary and treatment completion summary will be based on subjects who received study drug (Safety Set). Percentages will be calculated based on the Safety Set. These data will be

provided by randomized treatment groups. If a subject is rescreened because the subject has been a screen failure the first time, the status of the subject will be determined from the second screening. In the count of screened subjects, this subject will be counted only once.

The number and percentage of subjects will also be summarized for each reason for premature discontinuation. In addition, the number of subjects whose data should be used for the planned analyses will be identified for each respective analysis set (ie, All Subject, Safety, Efficacy, and PK Sets).

Study completion and discontinuation details, eligibility, treatment allocation, population assignment, and protocol deviations will be presented in listings.

9.2.2 Protocol Deviations

Protocol deviations identified during site monitoring will be captured on an electronic case report form (eCRF) and categorized by the study team as major and minor deviations, without any unblinding information. The major deviations will be further categorized as major-efficacy, major-safety and major-Good Clinical Practice (GCP) deviations. The major deviations will be summarized by type and by actual treatment received using the Safety Set. The minor deviations will be included in the listing.

The list of protocol deviations that may affect efficacy will be identified and finalized by a study team review before database unblinding by a study team review, and will be documented as such.

Any violation of inclusion/exclusion criteria will be presented in a data listing using the Randomized Set.

9.2.3 Demographics and Baseline Characteristics

Demographic data, such as age, gender, race and ethnicity, and baseline characteristics, such as height, weight, body mass index (body mass index [BMI], calculated as weight (kg)/[height (m)²]), and baseline antidepressants use, will be listed and summarized using the Safety Set. For this summary, as well as for the subsequent analyses, baseline antidepressant use will be defined as taking any medications belonging to the anatomical therapeutic chemical (ATC) 3 term N06A or N05A, or contain terms as ‘depression’, ‘postpartum depression’, ‘major depression’, postpartum depression (‘PPD’), ‘major depressive disorder’, or ‘major depressive mood’.

Drug and alcohol, and pregnancy screening results will be collected and listed but not summarized, as they are considered part of the inclusion/exclusion criteria.

9.2.4 Medical History

Medical history collected at screening will be coded using the Medical Dictionary for Regulatory Activities (MedDRA), Version 23.0. Medical history data will be summarized by system organ class (SOC) and preferred term (PT) and listed by subject using the Safety Set.

9.2.5 Study Drug Exposure and Compliance

Drug administration information collected on the eCRF will be listed by subject using the Safety Set. Details will include dose, infusion rate and unit, start date/time of dose, and end

Statistical Analysis Plan (Methods)
Study 547-PPD-304

Sage Therapeutics, Inc.
CONFIDENTIAL

date/time of dose. In Protocol Version 1.0-2.0, fusion administration sets were fully primed with admixture according to subject body weight, so the infusion rate for each infusion duration is fixed. In Protocol Version 3.0 and 4.0, the infusion administration set was set as the same, but the infusion rates vary depending on subject body weight, with the target 1mg/mL concentration to achieve the recommended dose for each infusion duration. The dose categories and infusion rate for given dose are listed in [Table 2](#).

Table 2: Dose Categories and Infusion Rate for Given Dose of 547-PPD-304

Dose Category	Infusion Rate for Given Dose (mcg/kg/hour)	
Titration	30 (Day 1 0-4 hours)	60 (Day 1 4-24 hours)
Maintenance	90 (Day 2 24 hours - Day 3 52 hours)	
Taper	60 (Day 3 52-56 hours)	30 (Day 3 56-60 hours)

Overall exposure to study drug is defined as total number of hours treated with study drug during the study, which is calculated as the sum of actual exposure duration of each infusion segment. The exposure duration for a segment is defined as (end time of infusion – start time of infusion [in seconds])/3600.

Exposure to study drug in each planned infusion rate segment (titration dose, maintenance dose, and tapering dose) is defined as the sum of actual exposure duration of each infusion segment within the infusion rate segment.

Study drug compliance (%) is calculated as [actual total dose (in mcg/kg)/planned total dose (in mcg/kg)] x 100.

Overall exposure to study drug, exposure to study drug in each infusion rate segment and study drug compliance will be summarized using the Safety Set.

9.3 Efficacy Analysis

All efficacy analyses will be performed for the Efficacy Set unless otherwise specified.

9.3.1 Definition of Efficacy Variables

[REDACTED]

Statistical Analysis Plan (Methods) Study 547-PPD-304

Sage Therapeutics, Inc.
CONFIDENTIAL

Statistical Analysis Plan (Methods) Study 547-PPD-304

Sage Therapeutics, Inc.
CONFIDENTIAL

Statistical Analysis Plan (Methods) Study 547-PPD-304

Sage Therapeutics, Inc.
CONFIDENTIAL

Statistical Analysis Plan (Methods)
Study 547-PPD-304Sage Therapeutics, Inc.
CONFIDENTIAL

9.3.3 Visit Windows

The unscheduled or early termination (ET) visit will be mapped to a scheduled visit for analysis using the date/time of collection/assessment as a basis to determine study day/hour and then study day/hour will be mapped to the intended visit. Once analysis visit windows get assigned, all visits, including scheduled visits, unscheduled visits, and ET visits will be eligible for being flagged as the “analyzed record” within the analysis window. A subject’s individual analysis visit window could potentially contain more than 1 visit. In the event of multiple visits falling within an analysis window or in case of a tie, the following rules will be used in sequence to determine the “analyzed record” for the analysis visit window:

- If there is a scheduled visit/day for the analysis visit window, then the scheduled visit/day data will be used.
- If there is no scheduled visit/day for the analysis visit window, the data closest to the scheduled study day/hour will be used.
- If there is no scheduled visit/day for the analysis visit window and there are visits equally close to the day/hour of scheduled visit, the latest data will be used.

[figure not shown]
The data not flagged as the “analyzed record” will also be listed in subject listings.

The Follow-up Period in this version of the protocol was reduced from Day 90 ± 7 days to Day 30 ± 3 days for consistency with the Follow-up Period in the adult PPD studies for brexanolone.

Statistical Analysis Plan (Methods)
Study 547-PPD-304

Sage Therapeutics, Inc.
CONFIDENTIAL

Tables 4 – 8 summarize the visit window for all the efficacy endpoint under both follow up schedules.

[figure not shown]
Statistical Analysis Plan (Methods)
Study 547-PPD-304

Sage Therapeutics, Inc.
CONFIDENTIAL

Statistical Analysis Plan (Methods)
Study 547-PPD-304

Sage Therapeutics, Inc.
CONFIDENTIAL

Statistical Analysis Plan (Methods)
Study 547-PPD-304

Sage Therapeutics, Inc.
CONFIDENTIAL

